12. EFFICACY PARAMETERS

Efficacy parameters will be listed for the mITT population. For the family of primary efficacy endpoints, summaries and analyses will be done using the mITT population unless otherwise noted. For secondary efficacy endpoints, complete-cases analyses will be done using the mITT population, whereby for each endpoint only subjects with complete data are included. Results from statistical analyses of treatment group differences in secondary endpoints may be reported to aid in interpretation and to assist in the design of future clinical trials.

12.1 Bulging TM

The presence/absence of bulging TM will be evaluated as part of the ear examination (see Section 11.4) done at each study visit; each ear will be evaluated separately.

A listing of bulging TM will be produced separately from the listing of ear examination parameters noted in Section 11.4.

Endpoints

The definition of bulging TM will be presence of 1+, 2+, or 3+ bulging on ear examination. Note: at least mild bulging is an inclusion criterion.

No bulging TM at the Day 4 visit is one of two endpoints in the primary efficacy endpoint family (see Section 13.5). The hypothesis set to be tested is:

Confidential Page 22 of 35

$$\begin{aligned} &H_o \colon P_A = P_P \\ &vs. \\ &H_A \colon P_A \neq P_P \end{aligned}$$

where P_A and P_P are the population proportions for OP0201 and placebo, respectively, for no bulging TM 4 days after the start of a 10-day treatment regimen.

The following sensitivity analyses will be done:

- PP analysis population
- Complete case (ie, mITT subjects who completed the Day 4 visit; see Section 13.3)
- Complete case with the endpoint defined as no bulging TM at the Day 4 visit and no recurrence of bulging TM (see Section 12.7) throughout the remainder of the study, assessed at the Day 28 visit. In this instance, "complete case" is equivalent to mITT subjects who completed the Day 28 visit.

No bulging TM assessed at the Day 12 and Day 28 visits are secondary endpoints.

Summaries and Analyses (see Section 13)

No bulging TM will be summarized and analyzed separately by visit using logistic regression. Summary tables will include frequencies and percentages of no bulging TM for each treatment group by visit and p-values for the differences. Crude rates of no bulging TM by treatment group and visit will be graphically displayed using bar charts.

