## 4.2 Scientific Rationale for Study Design

Otitis media is a very common disease seen in pediatric practice and in the US, it is the most common reason children are prescribed antibiotics. Otitis media is a serious condition that can result in life-long adverse consequences including irreversible hearing loss. Morbidity from otitis media is driven by recurrence and/or persistence of otitis media, as well as disease progression that leads to ruptured TM and/or damage to structures of the middle ear. Both intratemporal and intracranial complications can occur resulting in serious consequences and, in rare cases, death. More than \$5 billion is spent annually in the US on management of pediatric otitis media (IB).

Novus Therapeutics, Inc. is developing OP0201, a drug-device combination product comprised of 2 surfactant active ingredients DPPC and CP suspended in propellant (HFA-134a) to both treat and prevent otitis media. Both DPPC and CP are highly endogenous surfactants in the human respiratory tract. The product is administered via an intranasal pMDI. Together these 2 active ingredients effectively absorb the mucosal air-liquid interface and reduce the interfacial surface tension and passive opening pressure of the ET to promote “de-sticking” and restoration of physiologic activity of the ET. In the setting of inflammation in the nasopharynx, the ET fails to open as it should and therefore the middle ear is not ventilated.

This study will be conducted in the very young pediatric population (6 to 24 months, inclusive) as the targeted disease occurs more frequently in this age group, and the risk to this population from the compound (given in addition to a course of antibiotics), which is found naturally in human tissues, is considered to be very low. Parents/caregivers will be instructed to contact the Investigators if concerned about the Participant’s status. The use of randomization, a placebo and blinding are employed in this study to eliminate bias in evaluating safety, tolerability, and efficacy.

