### 5.1 Inclusion Criteria

Participants are eligible to be included in the study only if all the following criteria apply:

3. Male and female infants and children aged 6 to 24 months (inclusive).
4. Diagnosis of AOM - moderate to severe bulging of the TM (Key Action Statement 1A), or mild bulging of TM and recent (less than 48 hours) onset of ear pain (otalgia) (Key Action Statement 1B), or mild bulging of the TM and intense erythema of the TM (Key Action Statement 1B).
5. Score of 5 or more on the 5-question version of the AOM-SOS scale.
6. Intact TM in both ears (eg, no perforation).
7. Written informed consent by the infant/child's parent/legal guardian and their willingness to ensure that study instructions are followed, all study-related visits are attended, that treatment administration is given, and the parent/caregiver assessments are recorded according to the study protocol.
8. Parent/Legal Guardian has a smartphone or internet access to receive the electronic survey.

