### 8.1 Efficacy Assessments

Pneumatic otoscopy\* to evaluate each TM for:

- TM: intact, perforated
- Color (check all that apply): gray, pink, pale yellow, white, amber, blue
- Translucency: translucent, opaque, semi-opaque
- Mobility: none, 1+, 2+, 3+, 4+
- Air fluid interface: yes, no
- Distinct erythema: yes, no
- Position: neutral, retracted, 1+ bulging, 2+ bulging, 3+ bulging
- Otorrhea: no, serous, purulent

\*Note: Trained otoscopists who have undergone comprehensive educational program (ePROM, enhancing proficiency in otitis media) for training in the diagnosis of AOM will perform the otoscopy assessments in this study. This training includes training on cerumen removal, which is required (as needed) prior to performing pneumatic otoscopy.

Tympanometry will be performed, when possible, to assess middle ear function (ie, TM mobility, ET function) by measuring the amount of sound energy reflected back when a small probe is placed in each ear canal. The output of the right ear and left ear tympanometry will be a

tympanogram tracing recorded using a 226 Hz probe tone and a positive (+300 decaPascals [daPa]) to negative (-600 daPa) air-pressure sweep at fast speed. Each tympanogram will be classified as Type A (normal), Type B (abnormal), or Type C (abnormal).

AOM-SOS score will be recorded daily by parent/caregiver during the 10-day course of study treatment and antibiotics, and recorded in-clinic at Day 4, Day 12, and Day 28.

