4.2.2 Primary Efficacy Endpoint Family

The primary efficacy endpoint family is comprised of the following endpoints:

- No bulging of the TM assessed at the Day 4 visit by pneumatic otoscopy
- No MEE (OME) assessed at the Day 12 visit by pneumatic otoscopy

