11.4 Ear Examination

Examination of each ear will be done at each study visit. Summaries, by ear and visit, will be done for: TM findings (intact, perforated,), color (gray, pink, pale yellow, white, amber, blue), translucency (translucent, semi-opaque, opaque), mobility (none, 1+, 2+, 3+, 4+), air fluid interface (yes, no), otalgia (yes, no), distinct erythema (yes, no), position of the TM (neutral, retracted, 1+ bulging, 2+ bulging, 3+ bulging), otorrhea (no, serous, purulent), and diagnosis (no effusion, OME, AOM).

Confidential Page 21 of 35

Shift tables will summarize changes from baseline in normal/abnormal status, where "abnormal" will be limited to "definitely abnormal" defined as follows:

• TM findings: perforated

• Color: pale yellow, white, amber, blue

• Translucency: semi-opaque or opaque

• Mobility: none

• Air fluid interface: yes

• Otalgia: yes

• Distinct erythema: yes

• Position of TM: retracted, 1+ bulging, 2+ bulging, 3+ bulging

• Otorrhea: serous, purulent

Diagnosis: AOM, OME

Parameters will be summarized within treatment group for (a) first or only affected ear and (b) second or non-affected ear. Since either one ear or both ears can have AOM at baseline, this approach will allow descriptive comparisons between OP0201 and placebo treatment groups on number of affected ears (ie, one or both ears) and shifts from baseline, by visit, for both affected and non-affected ears at baseline.

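### A newly perforated or draining ear recorded as neutral or retracted counts as a Day 4 primary success, and no planned analysis tests the effect

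*SAP*

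**What the plan says.** The first member of the primary family (SAP 4.2.2) is "No bulging of the TM assessed at the Day 4 visit by pneumatic otoscopy". SAP 12.1 makes it operational: "The definition of bulging TM will be presence of 1+, 2+, or 3+ bulging on ear examination". Whatever is not one of those three grades is not bulging.

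Protocol 8.1 lists the otoscopy fields, including:

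- "TM: intact, perforated"
- "Position: neutral, retracted, 1+ bulging, 2+ bulging, 3+ bulging"
- "Otorrhea: no, serous, purulent"

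Position has no level for a perforated or unassessable eardrum. SAP 11.4 repeats these fields and adds a diagnosis field (no effusion, OME, AOM). Its list of definitely abnormal findings for the shift tables includes "TM findings: perforated" and both serous and purulent otorrhea.

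Protocol 5.1 requires both eardrums to be intact at entry. Protocol 1.1 and 2.1 present absence of bulging at Day 4 as the evidence that the acute otitis has resolved. SAP 12.1 evaluates each ear separately and does not say how two ears combine into one result for the child. Its three Day 4 sensitivity analyses are per protocol, complete case, and complete case with no later recurrence of bulging. SAP 13.3 imputes a missing primary outcome from the observed response distribution of the child's own arm.

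**The concern.** An eardrum may stop bulging because the effusion has resolved, or because the drum has ruptured and the middle ear has drained. The position code does not separate the two. Because entry requires intact drums, a perforation seen at Day 4 is new. The same ear can then be definitely abnormal in the safety tables, and even carry a recorded diagnosis of AOM, while the child is a responder in the primary analysis.

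Under SAP 13.4, either primary endpoint is enough to conclude efficacy, so Day 4 can carry the trial alone. If such ears are commoner on placebo, part of a real benefit is hidden. If they are commoner on OP0201, part of the apparent benefit is not resolution. The Day 12 and Day 28 no-bulging secondary endpoints use the same definition.

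**Working it through.** **How one child is scored.** Take a child with a new perforation at Day 4 and no bulge in the other ear.

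| Position recorded for the perforated ear | Day 4 result under SAP 12.1 and 13.3 |
|---|---|
| 1+, 2+ or 3+ bulging | Failure |
| Neutral or retracted | Success |
| Blank | Missing and imputed; at the planning rates a success in about 40% (placebo) or 65% (OP0201) of imputations |

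The per-protocol and complete-case analyses change who is included, and the third adds later recurrence of bulging. All three keep the position-only rule.

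**The plan's power figure.** Inputs from SAP 5: 70 per arm, 10% dropout (70 × 0.9 = 63 observed), 0.40 against 0.65 at Day 4, 0.30 against 0.55 at Day 12, two-sided Pearson chi-square, Hochberg. By normal approximation, power at 0.05 and 0.025 is 0.810 and 0.721 (Day 4) and 0.818 and 0.731 (Day 12). With the endpoints taken as independent, the probability that at least one succeeds is

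0.721 + 0.731 − 0.721 × 0.731 + (0.810 − 0.721) × (0.818 − 0.731) = 0.933.

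Exact enumeration gives 0.937. The stated 93% reproduces, so the scoring issue does not make it wrong.

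**Size of the effect.** Let q be the share of all children in an arm who are perforated or draining but coded non-bulging. The documents give no value; 2% and 5% are assumptions.

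- Children per arm: 0.02 × 70 = 1.4 and 0.05 × 70 = 3.5. Each moves the arm's rate by 1/70 = 1.4 points.
- Share of recorded successes that are not resolution, on placebo: 0.02/0.40 = 5% and 0.05/0.40 = 12.5%. On OP0201: 0.02/0.65 = 3.1% and 0.05/0.65 = 7.7%.
- Bias in the Day 4 difference: q on OP0201 minus q on placebo.

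Re-scoring these children as failures, where the planning rates had counted them as successes (63 per arm; Day 4 power by normal approximation, family power by exact enumeration with independent endpoints):

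| q placebo | q OP0201 | Re-scored rates | Difference | Day 4 power at 0.05 | Power for at least one endpoint |
|---|---|---|---|---|---|
| 0 | 0 | 0.40, 0.65 | 0.25 | 81.0% | 93.7% |
| 2% | 2% | 0.38, 0.63 | 0.25 | 80.9% | 93.7% |
| 5% | 5% | 0.35, 0.60 | 0.25 | 81.0% | 93.7% |
| 0 | 5% | 0.40, 0.60 | 0.20 | 61.4% | 88.2% |
| 5% | 0 | 0.35, 0.65 | 0.30 | 93.0% | 97.4% |

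**False positives.** Suppose true resolution is 40% in both arms and OP0201 has an excess d of such ears. The position-only rates are then 0.40 and 0.40 + d. Exact enumeration of the Pearson test with 63 per arm gives these rejection rates at 0.05:

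- d = 0: 5.6%
- d = 2 points: 6.3%
- d = 5 points: 9.8%

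At 0.025, the level Hochberg applies when Day 12 is not significant, the last two are 2.8% and 4.9%. The SAP's final test is a covariate-adjusted logistic regression, so these are guides.

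**The case against.** The SAP implements the protocol endpoint faithfully. Protocol 3.1 chose absence of bulging because bulging is the hallmark sign, and the 40% placebo rate and 0.25 difference were set for that sign alone. Adding perforation and otorrhea makes a composite. This stands as a cost of the fix, and it is why a prespecified sensitivity analysis is an acceptable fallback.

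Four stronger readings are tempting, but the documents do not support them.

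- *A perforated ear cannot be coded as bulging, so every perforation is a success.* Status and position are separate fields and nothing bars both codes. An ear coded perforated and 1+ is a failure, and a blank position is imputed.
- *Treatment failure and clinical success are computed so as to miss perforation.* SAP 12.5 and 12.6 take both from the eCRF and do not derive them. Only their written criteria leave perforation out.
- *The plan already classes a Day 4 perforation as non-response.* Protocol 4.2 mentions "disease progression that leads to ruptured TM and/or damage to structures of the middle ear", but as general background on morbidity. The SAP 11.4 list serves the safety shift tables and also calls a retracted drum and an OME diagnosis abnormal, and both are compatible with no bulging.
- *The plan conceals the event.* Perforation and otorrhea are summarized by arm and visit in Tables 14.3.9.3.1 and 14.3.9.3.2, and eardrum examination is a safety endpoint. An excess on OP0201 would be visible there, though not reflected in the primary result.

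**Conclusion.** The point holds as a scoring gap in the primary endpoint. Under SAP 12.1, a child with a newly perforated or draining ear recorded as neutral or retracted, and no bulging in the other ear, is a Day 4 success, and no planned Day 4 sensitivity analysis shows what that does to the result. This assumes that both ears must be free of bulging for the child to succeed, which the SAP does not state.

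The size cannot be fixed from the documents. With equal rates by arm, the difference stays at 0.25 and power is essentially unchanged, but at an assumed 5% one in eight placebo successes is not resolution. With unequal rates, the bias equals the difference in rates, and its direction depends on which arm has more. An assumed excess of 2 to 5 points on OP0201 with no true effect raises Day 4 rejection at 0.05 from 5.6% to between 6.3% and 9.8%. This is worth correcting while the data are blinded; it does not invalidate the design.

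**What to change.** Before unblinding, amend SAP 12.1 for Day 4, and for the Day 12 and Day 28 no-bulging endpoints, as follows:

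1. Score a child with a new perforation or otorrhea in either ear at the visit as a non-responder, whatever the position code and also when position is unrecorded.
2. State whether serous as well as purulent otorrhea counts, since SAP 11.4 classes both as abnormal.
3. State the child-level rule: both ears must meet the criterion.
4. Report the position-only definition alongside and declare the change in SAP 16.

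If the sponsor keeps the literal protocol endpoint as primary, make the version that scores perforation and otorrhea as failure a prespecified sensitivity analysis, and still state items 2 and 3 and how an unrecorded position is handled.

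The cost is some SAP text and one derivation from fields already collected at every visit. The downside is a small declared departure from the endpoint for which the 40% placebo rate and 0.25 difference were set, and possibly slightly lower response rates in both arms.

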### 9.4.1 Efficacy Analyses

The analysis of the primary efficacy endpoint family will compare the 2 treatment groups (OP0201, placebo) with respect to the proportion of Participants with no bulging of the TM at the Day 4 Visit as well as the proportion of Participants with no MEE at the Day 12 Visit using the ITT population for which Participants with missing data at the Day 4 Visit will be considered as having bulging TM and those with missing data at the Day 12 Visit will be considered as having MEE. A sensitivity analysis will be done that defines the endpoints as no bulging of the TM at the Day 4 Visit and no recurrence of bulging TM throughout the remainder of the study, and no MEE at the Day 12 Visit and no recurrence of MEE throughout the remainder of the study. Sensitivity analyses will also be done using the per-protocol population. Treatment groups will be statistically compared using generalized estimating equations (GEE), if possible, with an alternative method (eg, logistic regression) at each visit as an alternative if GEE convergence cannot be achieved. Randomization stratifiers (daycare attendance [yes, no] and age group [ $\geq 6$  to  $<12$  months,  $\geq 12$  to  $\leq 24$  months]) and degree of TM bulging at baseline will be covariates. Tympanic membrane bulging at baseline will also be evaluated as a potential effect modifier.

The step-up Hochberg procedure will be used to control the familywise Type 1 error. Specifically, the endpoint with the highest p-value will be tested first at the 0.05 significance

level and, if significant, both endpoints will be declared significant; if the endpoint with the highest p-value is not significant at the 0.05 level, the other endpoint will be tested at the 0.025 significance level. A positive treatment effect on efficacy will be concluded if at least 1 of the 2 endpoints in the primary efficacy endpoint family is significant

Descriptive statistics will be provided for the primary efficacy endpoint family by the following sub-groups: age stratum ( $\geq 6$  to  $< 12$  months,  $\geq 12$  to  $\leq 24$  months), race (Caucasian, non-Caucasian), gender (male, female), laterality of disease (unilateral, bilateral), history of recurrent AOM defined as 3 or more episodes in the preceding 6 months or 4 or more episodes over the course of 12 months (yes, no), and daycare attendance stratum defined as exposure to 3 or more children outside of the home for 10 or more hours per week (yes, no).

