12.7 AOM Recurrence

AOM recurrence will be defined as clinical success at the Day 12 visit and return for an interim/sick visit Day 17 through Day 28 (including the Day 28 visit, which can be out-of-window) with AOM at that visit. Clinical success is defined as in Section 12.6.

AOM recurrence status will be shown in a listing.

Endpoints

AOM recurrence will be a secondary endpoint and will be assessed using the subset of the mITT population that achieved clinical success at the Day 12 visit. Subjects in this subset who did not have an interim/sick visit Day 17 through Day 28 at which AOM was diagnosed and who discontinued the study before Day 28 will be excluded from summaries and analyses.

Summaries and Analyses (see Section 13)

Confidential Page 26 of 35

AOM recurrence will be analyzed using logistic regression. A summary table will include frequencies and percentages of recurrence and a p-value for the treatment group difference.

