APPENDIX B: TABLES OF CONTENTS FOR TABLES, FIGURES, AND LISTINGS

TABLES

NUMBER	TITLE	POPULATION
Study Popula	tion	
14.1.1	Subject Disposition	all randomized
14.1.2	Eligibility	all randomized
14.1.3	Reasons for Screen Failure	Screened excluding
		randomized
14.1.4	Protocol Deviations	all randomized
14.1.5	Analysis Populations	all randomized
14.1.6	Baseline Characteristics	all randomized
14.1.7.1	Medical History	all randomized
14.1.7.2	Baseline Symptoms	all randomized
14.1.8	Pre-Treatment Adverse Events	Screened
Treatments		
14.1.9.1	Study Treatment Exposure	Safety
14.1.9.2.1	Study Treatment Compliance	Safety
14.1.9.2.2	Oral Antibiotic Compliance	Safety
14.1.10.1	Prior Medications	all randomized
14.1.10.2	Concomitant Medications	Safety
Efficacy Endp	oints	
14.2.1.1	Bulging TM	mITT
14.2.1.2	Bulging TM	Per Protocol
14.2.1.3	Bulging TM	Complete Case
14.2.1.4	Bulging TM and No Recurrence	mITT
14.2.1.5	Bulging TM by age group	mITT
14.2.1.6	Bulging TM by sex	mITT
14.2.1.7	Bulging TM by race	mITT
14.2.1.8	Bulging TM by disease laterality	mITT
14.2.1.9	Bulging TM by history of recurrent AOM	mITT
14.2.1.10	Bulging TM by daycare attendance	mITT
14.2.1.11.1	Bulging TM by study site	mITT
14.2.2.1	MEE	mITT
14.2.2.2	MEE	Per Protocol
14.2.2.3	MEE	Complete Case
14.2.2.4	MEE and No Recurrence	mITT
14.2.2.5	MEE by age group	mITT
14.2.2.6	MEE by sex	mITT
14.2.2.7	MEE by race	mITT
14.2.2.8	MEE by disease laterality	mITT
14.2.2.9	MEE by history of recurrent AOM	mITT
14.2.2.10	MEE by daycare attendance	mITT
14.2.2.11.1	MEE by study site	mITT
14.2.3.1	Tympanogram Shifts from Baseline	Tympanogram Subset
14.2.4.1	AOM-SOS Scale Score – 10-Day Mean	mITT
14.2.5.1.1	AOM Cure	mITT

Confidential Page 32 of 35

14.2.5.1.2	AOM Cure – Sensitivity Analysis	mITT
14.2.6.1	AOM-SOS Response	mITT
14.2.7.1	AOM Treatment Failure, AOM Relapse, AOM Recurrence	mITT
Safety Endp	oints	
14.3.1.1	Summary of TEAE Incidence	Safety
14.3.1.2.1	Incidence of TEAEs by System Organ Class (SOC) and Preferred Term (PT)	Safety
14.3.1.2.2	Incidence of TEAEs Related to Study Treatment by SOC and PT	Safety
14.3.1.2.3	Incidence of TEAEs by Severity, by SOC and PT	Safety
14.3.1.2.4	TEAEs by PT in Descending Order of Incidence	Safety
14.3.1.3.1	Incidence of TESAEs by SOC and PT	Safety
14.3.1.3.2	Incidence of TESAEs Related to Study Treatment by SOC and PT	Safety
14.3.1.3.3	TESAEs by PT in Descending Order of Incidence	Safety
14.3.1.4	Non-TEAEs	Safety
14.3.9.1	Vital Signs, Observed Values and Changes from Baseline	Safety

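### SAP 12.1 contradicts itself and the protocol on what counts as recurrence in the sustained no-bulging sensitivity analysis, so a child who bulges again at Day 12 can be classed as sustained

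*SAP*

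**What the plan says.** Protocol 9.4.1 defines the sensitivity endpoint as "no bulging of the TM at the Day 4 Visit and no recurrence of bulging TM throughout the remainder of the study". It sets no Day 28 limit and makes no reference to AOM recurrence.

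SAP 12.1 asks for no bulging at Day 4 and, with a pointer to Section 12.7, no recurrence of bulging "throughout the remainder of the study, assessed at the Day 28 visit". It limits the analysis to a complete-case set that "is equivalent to mITT subjects who completed the Day 28 visit". The same section sets the threshold for bulging: "The definition of bulging TM will be presence of 1+, 2+, or 3+ bulging on ear examination".

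The section it points to, SAP 12.7, reads: "AOM recurrence will be defined as clinical success at the Day 12 visit and return for an interim/sick visit Day 17 through Day 28", with the qualification "including the Day 28 visit, which can be out-of-window) with AOM at that visit". Clinical success is taken from SAP 12.6. It is lost with moderate to severe bulging, or with mild bulging plus recent otalgia or intense erythema. Mild bulging alone still counts as success.

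Three other places bear on the point:
- SAP 12.2 has the parallel MEE analysis, without a Day 28 clause and without the 12.7 reference, but also restricted to Day 28 completers.
- SAP Appendix B lists Table 14.2.1.4, "Bulging TM and No Recurrence", and its MEE counterpart 14.2.2.4 under mITT, while Tables 14.2.1.3 and 14.2.2.3 are listed under Complete Case.
- SAP Section 16, the list of changes from the protocol, does not mention a narrower definition of recurrence.

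**The concern.** This analysis asks whether a Day 4 success lasts. The protocol's Amendment 2 history traces it to a suggestion from FDA biostatisticians. The SAP keeps the protocol's broad time span but adds two narrower clauses that a programmer could implement literally, and they are two different rules. One looks at the Day 28 visit. The other looks for AOM on Days 17 to 28, conditional on Day 12 status. Neither counts bulging at the Day 12 visit as a failure.

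The completer restriction adds a second gap: a child with documented re-bulging who leaves before Day 28 is dropped from the analysis and not counted as a failure. If either narrow clause is followed, durability will be overstated.

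**Working it through.** **The classification rules side by side.** Take a child with no bulging at Day 4 who completes Day 28, and apply the three readings of the SAP sentence. In the table, mild means 1+ bulging without recent otalgia or intense erythema.

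| Day 12 | Day 28 | Whole remainder of study (protocol) | Day 28 visit | Section 12.7 |
|---|---|---|---|---|
| clear | clear | sustained | sustained | sustained |
| clear | mild | not sustained | not sustained | **sustained** |
| clear | AOM | not sustained | not sustained | not sustained |
| mild | clear | not sustained | **sustained** | **sustained** |
| moderate to severe | clear | not sustained | **sustained** | **sustained** |
| moderate to severe | AOM | not sustained | not sustained | **sustained** |

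Bold cells differ from the protocol. The last row arises because a child with moderate to severe bulging at Day 12 is not a clinical success, so can never be a 12.7 recurrence. The second row arises because 12.7 requires AOM, whereas 12.1 counts any bulging of 1+ or more.

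**Interim visits.** SAP 8.7 excludes otoscopy that falls outside Days 4-6, 12-14 and 26-30, and keeps one observation per window. Bulging at a sick visit on Days 7-11 or 15-25 is therefore lost even if the broad phrase is followed, unless an exception is written.

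**Size.** The plan states no figure for this endpoint. The inputs come from SAP Section 5: 70 per arm, 40% of placebo children with no bulging at Day 4, and a difference of 0.25, hence 65% on OP0201. As a check on those inputs, the 93% power stated there reproduces as 93.3%, with 70 × 0.9 = 63 evaluable per arm and the two endpoints treated as independent.

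The share q of Day 4 responders who bulge again and are clear by Day 28 is not in the documents. I assume 5% to 15%.

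- Misclassified children = 70 × Day 4 response × q.
- OP0201: 70 × 0.65 = 45.5; × 0.05 = 2.3; × 0.15 = 6.8. As a share of 70: 3.25 to 9.75 points.
- Placebo: 70 × 0.40 = 28; × 0.05 = 1.4; × 0.15 = 4.2. As a share of 70: 2.0 to 6.0 points.
- Inflation of the difference with equal q: 3.25 − 2.0 = 1.25 points, to 9.75 − 6.0 = 3.75 points, in favour of OP0201.
- With unequal q the shift runs from 3.25 − 6.0 = −2.75 points (5% on OP0201, 15% on placebo) to 9.75 − 2.0 = +7.75 points (the reverse).

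These counts are before dropout and before exclusion of the first 3 subjects. At 10% dropout the counts fall by a tenth. The points stay the same if dropout is unrelated to outcome.

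**The case against.** The strongest reply is that the SAP sentence still covers the rest of the study. On that view the Day 28 clause only says when status is finalised, which fits the completer set, and a child bulging at Day 12 fails as the protocol intends. This stands in part. A reader might infer that the SAP looks at Day 28 only and cannot see earlier relapse. The text does not support that, because the broad phrase is in the same sentence. The defect is a contradiction, and either narrow clause gives the wrong classification if followed.

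The pointer to 12.7 may also be a slip. Other SAP cross-references are wrong: 12.1 and 12.2 cite a Section 13.5 that does not exist (multiplicity is in 13.4), and 8.5 sends missing data to 13.4 when it is in 13.3. That makes intent doubtful, but the pointer still needs correcting.

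Re-bulging is also visible elsewhere: no bulging at Day 12, treatment failure at Day 12 and AOM relapse before Day 17 are all analysed, and ear findings are tabulated by visit. So later relapse is not hidden. But these summaries do not identify which Day 4 responders bulged again, which is what the sustained endpoint measures.

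The mITT labels are a minor matter. Appendix B also labels the secondary-endpoint tables mITT although SAP 12 makes those analyses complete-case. Finally, this is one of three sensitivity analyses of one endpoint in an exploratory Phase 2a study, with no alpha attached. That limits the weight of the point.

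**Conclusion.** The point holds as an internal contradiction in SAP 12.1 and an undeclared departure from protocol 9.4.1. Under either narrow clause a child clear at Day 4, bulging at Day 12 and clear at Day 28 is classed as sustained. Section 12.7 adds two further errors, for moderate to severe bulging at Day 12 and for mild bulging alone at Day 28.

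The size rests on an assumed re-bulging rate of 5% to 15% and on the plan's Day 4 rates. A reader might apply the 65% response to both arms and infer 2 to 7 misclassified children in each. The plan puts placebo at 40%, so the placebo count is lower, and that gap is what inflates the difference by about 1.3 to 3.8 points. The direction depends on the re-bulging rate being similar in the two arms.

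Nothing here touches the primary test, the Hochberg procedure or type 1 error. Nor does the MEE analysis in 12.2 share the definition problem. Only the window rule and the completer restriction carry over to it.

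**What to change.** In SAP 12.1:
- Delete the reference to Section 12.7 and the clause that assesses recurrence at the Day 28 visit.
- Define recurrence as bulging of 1+ or more in any scheduled or interim ear examination after the Day 4 visit through study exit.
- Exempt these examinations from the Section 8.7 window exclusion and from its one-observation-per-window rule.
- Count documented recurrence as failure whether or not Day 28 was completed.
- State how a missing Day 12 examination is handled, and how children who leave early without documented recurrence are treated. Including early leavers only when they fail would itself bias the rate.

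In SAP 12.2, apply only the window exemption and the rule that documented recurrence is failure, for MEE after Day 12. Make the population labels of Tables 14.2.1.4 and 14.2.2.4 match the text.

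The cost is SAP wording and one derivation for each endpoint, before database lock. No new data are needed: ears are examined at every scheduled visit, and protocol 4.1 has applicable procedures at interim visits recorded in the eCRF. Otoscopy is not guaranteed at every sick visit, so the rule can use only the examinations that were done.
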